### **1.3. Sample Size and Power**

A total sample size of 75 subjects will be required for this study. Each of the 2 andecaliximab treated groups will be compared to the placebo group. A sample size of 25 per group will provide a power of 80% with a two-sided  $\alpha$  level of 0.05 to detect a Minimal Clinically Important Improvement (MCII) in DAS28(CRP) change from Baseline of 1.2 at Week 12 between a andecaliximab treated group and the placebo group, assuming a common standard deviation of 1.35 and 15% early dropout rate.

The study was terminated after 15 subjects had been enrolled. Therefore, no inferential analyses will be performed due to the small sample size.

## **2. TYPE OF ANALYSIS**

### **2.1. Interim Analyses**

Administrative interim analyses of efficacy and safety data were performed by the Gilead internal unblinded team. The purpose of the analyses was to assess efficacy of andecaliximab for further planning and development as a single agent and in combination. This unblinded team was independent of the GS-US-373-1499 study team who were not directly involved in routine study conducts. People who were unblinded were documented in the unblinded form GF-27011A, and the justification was documented in GT-27011A per SOP-BM-27011. The Study Team has remained blinded to treatment assignments throughout the trial until the database has been locked and unblinded.

### **2.2. Final Analysis**

Due to early termination of the study by the sponsor, the final analysis of the data will be performed for all enrolled subjects as of 05 June 2017. Final analysis will occur after outstanding data queries have been resolved or adjudicated as unresolvable, and the data have been cleaned and finalized.

### **3. GENERAL CONSIDERATIONS FOR DATA ANALYSES**

Analysis results will be presented using descriptive statistics. For categorical variables, the number and percentage of subjects in each category will be presented; for continuous variables, the number of subjects (n), mean, standard deviation (SD) or standard error (SE), median, first quartile (Q1), third quartile (Q3), minimum, and maximum will be presented.

By-subject listings will be presented for all subjects in the All Randomized Analysis Set and sorted by treatment group, subject identification (ID) number, visit date, and time (if applicable). Data collected on log forms, such as AEs, will be presented in chronological order within the subject. The treatment group to which subjects were randomized will be used in the listings. Age, sex at birth, race, and ethnicity will be included in the listings.

#### **3.1. Analysis Sets**

Analysis sets define the subjects to be included in an analysis. Analysis sets and their definitions are provided in this section. The analysis set will be identified and included as a subtitle of each TFL.

For each analysis set, the number and percentage of subjects eligible for inclusion will be summarized by treatment group.

##### **3.1.1. All Randomized Analysis Set**

All Randomized Analysis Set includes all subjects who are randomized in the study. This is the primary analysis set for by-subject listings.

##### **3.1.2. Full Analysis Set**

The Full Analysis Set (FAS) includes all randomized subjects who received at least 1 dose of study drug. The study drug in this study is andecaliximab and placebo-to-match for andecaliximab. This is the primary analysis set for efficacy analyses.

##### **3.1.3. Safety Analysis Set**

The Safety Analysis Set includes all subjects who received at least 1 dose of study drug. This is the primary analysis set for safety analyses.

### **3.2. Subject Grouping**

For analyses based on the All Randomized Analysis Set, FAS, subjects will be grouped according to the treatment to which they were randomized. For analyses based on the Safety Analysis Set, subjects will be grouped according to actual treatment received. The actual treatment received will differ from the randomized treatment only when their actual treatment differs from randomized treatment for the entire treatment duration.

### **3.3. Strata and Covariates**

No stratification factors or covariates will be used in the analyses supporting the synoptic CSR.

### **3.4. Examination of Subject Subgroups**

There will be no subgroup analyses for efficacy or safety.

### **3.5. Multiple Comparisons**

Adjustments for multiplicity will not be applied.

### **3.6. Missing Data and Outliers**

#### **3.6.1. Missing Data**

In general, missing data will not be imputed unless methods for handling missing data are specified. Exceptions are presented in this document.

For missing last dosing date of study drug, imputation rules are described in Section 4.2.1. The handling of missing or incomplete dates for AE onset is described in Section 7.1.5.2.

#### **3.6.2. Outliers**

Outliers will be identified during the data management and data analysis process, but no sensitivity analyses will be conducted. All data will be included in the data analyses.

### **3.7. Data Handling Conventions and Transformations**

In general, age (in years) on the date of the first dose of study drug will be used for analyses and presentation in listings. If an enrolled subject was not dosed with any study drug, the randomization date will be used instead of the first dosing date of study drug. For screen failures, the date the last informed consent was signed will be used for age calculation. If only birth year is collected on the case report form (CRF), “01 January” will be used for the unknown birth day and month for the purpose of age calculation. If only birth year and month are collected, “01” will be used for the unknown birth day.

Non-PK Data that are continuous in nature but are less than the lower limit of quantitation (LOQ) or above the upper LOQ will be imputed as follows:

- A value that is 1 unit less than the LOQ will be used to calculate descriptive statistics if the datum is reported in the form of “ $< x$ ” (where  $x$  is considered the LOQ). For example, if the values are reported as  $< 50$  and  $< 5.0$ , values of 49 and 4.9, respectively, will be used to calculate summary statistics. An exception to this rule is any value reported as  $< 1$  or  $< 0.1$ , etc. For values reported as  $< 1$  or  $< 0.1$ , a value of 0.9 or 0.09, respectively, will be used for calculate summary statistics.

- A value that is 1 unit above the LOQ will be used to calculate descriptive statistics if the datum is reported in the form of “> x” (where x is considered the LOQ). Values with decimal points will follow the same logic as above.
- The LOQ will be used to calculate descriptive statistics if the datum is reported in the form of “≤ x” or “≥ x” (where x is considered the LOQ).

### **3.8. Analysis Visit Windows**

#### **3.8.1. Definition of Study Day**

Study Day 1 is defined as the first dose date of study drug administration. The last dose date for the study drug will be the end date on study drug administration CRF for the record where the “study drug was permanently withdrawn” flag is “Yes”.

Study Day will be calculated from the Study Day 1 and derived as follows:

- For postdose study days: Assessment Date – Study Day 1 + 1
- For days prior to the first dose: Assessment Date – Study Day 1

For the outputs based on the study period (double-blind and OLE), the following rule will be applied:

- If subject continues into the OLE then the double-blind (DB) period reports will include the data collected prior to the date of the first dose of study drug in the OLE. The OLE summaries will include the data from the date of the first dose of OL treatment, inclusive.
- If subject does not continue into the OLE then all data collected starting from Day 1 will be included in the DB period summaries.

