#### **3.8.2. Analysis Visit Windows**

Subject visits may not occur on protocol-specified days. Therefore, for the purpose of analysis, observations will be assigned to analysis windows.

In general, the baseline value will be the last nonmissing value on or prior to the first dose date of study drug.

The analysis windows for joint count assessment, health assessment questionnaire - disability index (HAQ-DI), physician’s global assessment of disease activity (PhGA), patient’s global assessment of disease activity (PtGA), patient’s pain assessment, on-treatment CRP, SF-36, weight and vital signs are provided in Table 3-1. The analysis windows for safety laboratory data is provided in Table 3-2.

**Table 3-1. Analysis Visit Windows for Joint Count Assessment, HAQ-DI, PhGA, PtGA, Pain, On-Treatment CRP, SF-36, Weight and Vital Signs for Double-Blind Treatment**

Nominal Visit	Analysis Visit	Nominal Study Day	Lower Limit	Upper Limit
Baseline	DB Baseline	1	(none)	1
Week 1	DB Week 1	8	2	18
Week 4	DB Week 4	29	19	43
Week 8	DB Week 8	57	44	71
Week 12	DB Week12	85	72	Prior to or on the first dose date of OL if applicable

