#### 7.1.6. Summaries of Adverse Events and Deaths

Treatment-emergent AEs will be summarized based on the Safety Analysis Set.

The AEs will be reported by the treatment period. If subject does not continue into the OLE then all TEAEs will be reported in the DB treatment period (Day 1 to Week 12) summaries. For subjects who continue into the OLE, TEAEs during the DB treatment period are the AEs that started prior to the first dose of OL treatment. The AEs with the onset date on or after the first dose of the OL treatment and no later than 30 days after permanent discontinuation of study drug will be reported in the OLE summaries.

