### **7.2.1.       Summaries of Numeric Laboratory Results**

In the case of multiple values in an analysis window, data will be selected for analysis as described in Section 3.8.3.

Descriptive statistics for laboratory tests will not be presented.

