#### **7.2.2.2. Summaries of Laboratory Abnormalities**

The summaries (number and percentage of subjects) for treatment-emergent laboratory abnormalities will be provided by lab test, treatment group and treatment period; subjects will be categorized according to the most severe postbaseline abnormality grade for a given lab test. If subject does not continue into the OLE then all treatment-emergent laboratory abnormalities will be reported in the DB treatment period (Day 1 to Week 12) summary. For subjects who continue into the OLE, treatment-emergent laboratory abnormalities during the DB treatment period are the laboratory abnormalities that started prior to the first dose of OL treatment. The laboratory abnormalities with the onset date on or after the first dose of the OL treatment and no later than 30 days after permanent discontinuation of study drug will be reported in the OLE summary.

A by-subject listing of treatment-emergent Grade 3 or higher laboratory abnormalities will be provided by subject ID number and visit in chronological order. This listing will include all test results that were collected throughout the study for the lab test of interest, with all applicable severity grades displayed.

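### SAP 3.8.1 gives the first open-label dose date to the OLE while Tables 3-1 and 3-2 keep it in double-blind Week 12, so pre-dose Week 12 laboratory abnormalities can be counted in the wrong period

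*SAP*

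**What the plan says.** **Period rule.** SAP 3.8.1 covers outputs based on study period. For a subject who continues into the OLE, the double-blind (DB) "period reports will include the data collected prior to the date of the first dose of study drug in the OLE". The next sentence reads: "The OLE summaries will include the data from the date of the first dose of OL treatment, inclusive".

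**Visit windows.** In SAP 3.8.2, Table 3-1 (efficacy measures, on-treatment CRP, SF-36, weight, vital signs) and Table 3-2 (safety laboratory data) both give the upper limit of DB Week 12 as "Prior to or on the first dose date of OL if applicable". Table 3-2 opens its only open-label (OL) window at OL Day 2. The footnote counts the first OL dose date as OL Day 1, so that date has no OL window.

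**Laboratory table.** SAP 7.2.2.2 states that summaries for "treatment-emergent laboratory abnormalities will be provided by lab test, treatment group and treatment period". For OLE entrants, the DB abnormalities "are the laboratory abnormalities that started prior to the first dose of OL treatment". The OLE side is worded differently: "The laboratory abnormalities with the onset date on or after the first dose of the OL treatment", up to 30 days after permanent discontinuation. Each subject is classed by the most severe post-baseline grade for the test.

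**Timing.** The protocol synopsis, Section 6.4 and Appendix 2 footnote q place the first OL dose at the Week 12 visit, after that visit's blinded procedures. Appendix 2 lists hematology and chemistry at Week 12 in the blinded table. The OLE table starts them at Week 13.

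**The concern.** For an entrant who follows the schedule, the Week 12 draw and the first OL dose fall on one date, with the draw first. That sample reflects blinded treatment only. The period rule nevertheless sends it to the OLE, while the laboratory window calls it DB Week 12.

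All entrants receive 300 mg in the OLE, including those randomized to placebo (protocol 3.3.1). An abnormality that arose on blinded placebo or 150 mg could therefore be reported in the open-label 300 mg period although no OL dose had yet been given, and be missing from the DB summary. For a placebo subject, that is before any exposure to the active drug.

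Two programmers who each follow the SAP could produce different DB and OLE tables.

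**Working it through.** The plan states no figure to reproduce here. The check is to apply each rule to the same dates.

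**Inputs.** L is the study day of the laboratory sample and D the study day of the first OL dose. Week 12 is nominal Day 85 (Table 3-2). The visit window is ±3 days (protocol Appendix 2), so the visit falls between Day 85 − 3 = 82 and Day 85 + 3 = 88.

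**Rules.**
- SAP 3.8.1: DB if L < D; OLE if L ≥ D.
- Table 3-2: DB Week 12 if 58 ≤ L ≤ D. OL Day = L − D + 1, and the OL window needs OL Day ≥ 2, that is L ≥ D + 1.
- SAP 7.2.2.2: DB if the abnormality started before the dose; OLE if its onset date is on or after the dose.

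| L | D | 3.8.1 | Table 3-2 | 7.2.2.2 |
|---|---|---|---|---|
| 82 | 82 | OLE | DB Week 12 | DB by time, OLE by date |
| 85 | 85 | OLE | DB Week 12 | DB by time, OLE by date |
| 88 | 88 | OLE | DB Week 12 | DB by time, OLE by date |
| 84 | 85 | DB | DB Week 12 | DB |
| 85 | 87 | DB | DB Week 12 | DB |
| 86 | 85 | OLE | OL Week 1 (OL Day 2) | OLE |
| 92 | 85 | OLE | OL Week 1 (OL Day 8) | OLE |

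The rules disagree only when L = D, and they do so wherever in the visit window that date falls. In that case one pre-dose result can satisfy both sentences of 7.2.2.2, and no tie-break is given.

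**Draws removed.** Post-baseline hematology and chemistry are scheduled in the blinded period at Weeks 1, 4 and 12 (protocol 6.3 and Appendix 2), which is 3 draws. With L = D, 3.8.1 leaves 3 − 1 = 2 in DB, so 1/3 (33%) are removed.

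**Which abnormalities move.** Those first seen at the Week 12 draw move. So do those that began earlier and worsened there. If a test is abnormal at Week 4 and reaches a higher grade at Week 12, the DB worst grade is the Week 12 grade under Table 3-2 but the Week 4 grade under 3.8.1. The higher grade is then counted in the OLE.

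**Number of subjects.** SAP 1.3 gives 15 enrolled. The number entering the OLE is not stated, so the entrants with a shared date number between 0 and 15.

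**The case against.** The best defence is that the two rules do different jobs. The tables assign records to visits and 3.8.1 assigns them to periods. No by-visit laboratory summary exists in which they could collide, because SAP 7.2.1 says: "Descriptive statistics for laboratory tests will not be presented". The one exposed output has its own text in 7.2.2.2. Its DB sentence refers to the dose rather than the dose date, and a Week 12 draw done as the protocol requires precedes that dose. The OL window opening at OL Day 2 points the same way.

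Part of this stands. Misallocation is a possible result of following the SAP, not a certain one. It does not remove the conflict: the companion sentence in 7.2.2.2 speaks of onset date, and 3.8.1, which applies to any by-period output, says inclusive.

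A reader might also infer more than the documents support:
- **That Week 12 efficacy data drop out of the DB results.** SAP 6.2.3 and 6.3.1 summarize efficacy by visit or analysis visit, which most naturally follows Table 3-1.
- **That most of the blinded period loses laboratory coverage.** The long gap after the Week 4 draw is a feature of the hematology and chemistry schedule, which has no Week 8 draw under either rule. Urinalysis and hsCRP are scheduled at Week 8. The length of the gap does not measure misplaced abnormalities.
- **That the adverse event rule has the same fault.** SAP 7.1.6 has similar wording ("The AEs with the onset date on or after the first dose of the OL treatment"). However, the protocol does not place an event's onset before the injection, as it does the Week 12 draw, so assigning that date to the OLE is defensible.

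**Conclusion.** The contradiction holds and its severity is minor. On the date when the protocol plans both the blinded Week 12 draw and the first OL dose, 3.8.1 and Table 3-2 give opposite periods and 7.2.2.2 does not settle which applies. The effect is confined to the by-period laboratory abnormality table and to OLE entrants whose draw and dose share a date. Among these, it changes the result only for a subject whose abnormality first appears, or reaches its worst grade, at that draw. The documents do not show that any such case occurred.

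The consequence is limited further because the report is synoptic, no testing is planned, and the by-subject hematology and chemistry listings (SAP 7.2) let a reader trace a misplaced result. Confidence is high that the wording conflicts. Whether results would in fact be misplaced depends on which rule is programmed.

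**What to change.** - **SAP 3.8.1.** State that visit assessments and laboratory samples, scheduled or unscheduled, dated on or before the first OL dose date belong to the DB period, and those dated after it belong to the OLE. This matches Tables 3-1 and 3-2 and also confirms the handling of Week 12 efficacy.
- **SAP 7.2.2.2.** Replace the two sentences for OLE entrants with one derivation. The DB worst treatment-emergent grade comes from post-baseline samples dated on or before the first OL dose date. The OLE worst grade comes from samples dated after it, up to 30 days after permanent discontinuation of study drug. This handles worsening as well as first appearance and keeps the existing 30-day limit.
- **SAP 7.1.6.** Leave the adverse event rule unchanged.

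The cost is wording in two sections and the matching period derivation for laboratory records. No new data or clock times are needed, because the protocol requires the Week 12 procedures before dosing and schedules no OLE hematology or chemistry until Week 13. One small convention remains: an unscheduled sample taken after the injection on that date would count as DB, as it already does in Table 3-2.

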#### **3.8.2. Analysis Visit Windows**

Subject visits may not occur on protocol-specified days. Therefore, for the purpose of analysis, observations will be assigned to analysis windows.

In general, the baseline value will be the last nonmissing value on or prior to the first dose date of study drug.

The analysis windows for joint count assessment, health assessment questionnaire - disability index (HAQ-DI), physician’s global assessment of disease activity (PhGA), patient’s global assessment of disease activity (PtGA), patient’s pain assessment, on-treatment CRP, SF-36, weight and vital signs are provided in Table 3-1. The analysis windows for safety laboratory data is provided in Table 3-2.

**Table 3-1. Analysis Visit Windows for Joint Count Assessment, HAQ-DI, PhGA, PtGA, Pain, On-Treatment CRP, SF-36, Weight and Vital Signs for Double-Blind Treatment**

Nominal Visit	Analysis Visit	Nominal Study Day	Lower Limit	Upper Limit
Baseline	DB Baseline	1	(none)	1
Week 1	DB Week 1	8	2	18
Week 4	DB Week 4	29	19	43
Week 8	DB Week 8	57	44	71
Week 12	DB Week12	85	72	Prior to or on the first dose date of OL if applicable

**Table 3-2. Analysis Visit Windows for Safety Laboratory Data for Double-Blind and Open-Label Treatment**

Nominal Visit	Analysis Visit	Nominal Study Day	Lower Limit	Upper Limit
Baseline	DB Baseline	1	(none)	1
Week 1	DB Week 1	8	2	18
Week 4	DB Week 4	29	19	57
Week 12	DB Week 12	85	58	Prior to or on the first dose date of OL if applicable
Week 13	OL Week 1	OL Day 8*	OL Day 2*	≥ OL Day 8*

\* OL Day (for post OL dose) is defined as: Assessment Date – First OL Dose Date + 1

Data collected on 30-day follow-up visit will be summarized as a separate visit, and labeled as “30-Day Follow-up Visit”. Data obtained after last dose date plus 30 days will be excluded from the summaries, but will be included in the listings.

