8.6. Safety Analysis

All safety analyses will be performed using the safety analysis set.

Safety will be evaluated by assessment of clinical laboratory tests, physical examinations, vital signs measurements at various time points during the study, and by the documentation of AEs.

All safety data collected on or after the first dose of study drug administration up to 30 days after the last dose of study drug will be summarized by treatment group according to the study drug received.

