## **6.2. Primary Efficacy Endpoints**

### **6.2.1. Definition of the Primary Efficacy Endpoints**

The primary endpoint for the study is change from baseline in DAS28(CRP) at Week 12. The DAS28(CRP) score is calculated as follows:

$$DAS28(CRP) = 0.56\sqrt{TJC28} + 0.28\sqrt{SJC28} + 0.36 \ln(CRP + 1) + 0.014 \times PtGA + 0.96,$$

where

TJC28 = number of joints tender out of 28 joints

SJC28 = number of joints swollen out of 28 joints

CRP = CRP measurement in unit of mg/L

PtGA = patient's global assessment of disease activity on a 0-100 VAS

Higher DAS28(CRP) value indicates more severe disease activity.

DAS28(CRP) will be calculated only for the time points with all measurements available, ie, missing DAS28(CRP) components will not be imputed.

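### SAP 3.8.2 excludes data after last dose plus 30 days from the summaries without limiting this to safety data; it conflicts with SAP 3.8.1 and, read literally, can remove observed Week 12 DAS28(CRP) values

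*SAP*

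**What the plan says.** SAP 3.8.2 contains two window tables. Table 3-1 covers joint counts, the patient's global assessment and on-treatment CRP, which are the inputs to DAS28(CRP), together with HAQ-DI, SF-36, weight and vital signs. Table 3-2 covers safety laboratory data. Two sentences follow Table 3-2. The first says that data from the 30-day follow-up visit are summarised as a visit of their own. The second is: "Data obtained after last dose date plus 30 days will be excluded from the summaries, but will be included in the listings".

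Other passages bear on that sentence:

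- **SAP 3.8.1, last dose date.** "The last dose date for the study drug will be the end date on study drug administration CRF", taken from the record flagged as permanent withdrawal.
- **SAP 3.8.1, subjects who do not enter the OLE.** "all data collected starting from Day 1 will be included in the DB period summaries".
- **Protocol 8.6.** The data to be summarised are described as "All safety data collected on or after the first dose of study drug administration up to 30 days after the last dose". Protocol 8.5, on efficacy, sets no cut-off after the last dose and leaves the detail to the SAP.
- **SAP 3.1.2.** The Full Analysis Set (FAS) "includes all randomized subjects who received at least 1 dose of study drug".
- **SAP 3.6.1 and 6.2.1.** In general, "missing data will not be imputed unless methods for handling missing data are specified"; for the primary endpoint, "DAS28(CRP) will be calculated only for the time points with all measurements available, ie, missing DAS28(CRP) components will not be imputed".
- **Protocol 3.5.2 and 6.5.** Subjects who stop study drug are to be kept in study visits and procedures where medically appropriate.
- **Follow-up timing.** For a subject not entering the OLE, the Protocol Synopsis (Study Procedures) counts 30 days from the last dose. Protocol 6.3.1 counts 30 days from the Week 12 visit.

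**The concern.** The FAS needs only one dose, and the protocol asks sites to keep collecting data after study drug is stopped. A subject who stops early, stays in follow-up and attends Week 12 therefore has a primary-endpoint value. SAP 3.8.1 puts that value into the double-blind summaries. The 3.8.2 sentence, taken at its word, takes it out once more than 30 days have passed since the last dose.

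Because DAS28(CRP) is not imputed, an excluded value leaves the Week 12 summary of the primary endpoint and of both response endpoints (DAS28(CRP) ≤ 3.2 and < 2.6). OLE entrants are not touched at Week 12, because their last dose date is the later date of permanent withdrawal. The exclusion would thus fall only on subjects who stopped early.

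The same sentence can also cancel the one before it, which promises a summary of the follow-up visit.

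**Working it through.** **Inputs**

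- Weekly dosing, with 12 injections in the blinded period (Protocol 3.4) and none at Week 12 for subjects not entering the OLE (Protocol Appendix 2, footnote q).
- Visit windows of ±3 days at Week 12 and ±5 days at the 30-day follow-up (Protocol Appendix 2).
- SAP Week 12 analysis window opening on Day 72 (Table 3-1).

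**Formulas**

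Scheduled day of Week k = 7k + 1. Cut-off = last dose day + 30. A value is excluded if its day is later than the cut-off.

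**Check against the plan's own days.** 7×1+1 = 8, 7×4+1 = 29, 7×8+1 = 57 and 7×12+1 = 85. These match the nominal days in Table 3-1. The Week 12 visit range is 85 ± 3, or Days 82 to 88.

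**Week 12 DAS28(CRP), non-OLE subject, literal reading**

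| Last scheduled dose | Day | Cut-off | Days lost out of 82 to 88 |
|---|---|---|---|
| Week 3 | 22 | 52 | 7 of 7 |
| Week 6 | 43 | 73 | 7 of 7 |
| Week 7 | 50 | 80 | 7 of 7 |
| Week 8 | 57 | 87 | 1 of 7 (Day 88) |
| Week 9 | 64 | 94 | 0 of 7 |

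Thresholds by exact day:

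- The nominal Day 85 value is lost if the last dose was on or before Day 54 (54 + 30 = 84).
- The whole visit range is lost if it was on or before Day 51 (51 + 30 = 81).
- No value in the SAP Week 12 window can survive if it was on or before Day 41 (41 + 30 = 71). With a last dose between Days 42 and 51, only a visit earlier than the protocol's ±3 days could be kept.
- The nominal Week 8 value (Day 57) is lost as well if it was on or before Day 26 (26 + 30 = 56).

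The boundary is approximate because doses can move. Assume that the 3-day dosing window in Protocol 5.3 runs both ways. A Week 7 dose on Day 53 then gives cut-off Day 83 (5 of 7 days lost), and a Week 8 dose on Day 54 gives cut-off Day 84 (4 of 7 lost).

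**30-day follow-up visit, non-OLE completer**

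The last of 12 weekly doses is at Week 11: 7×11+1 = Day 78, so the cut-off is Day 108.

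| Timing rule | Nominal day | ±5-day window | Days lost |
|---|---|---|---|
| Synopsis: last dose + 30 | 78 + 30 = 108 | 103 to 113 | 109 to 113 (5 of 11) |
| Protocol 6.3.1: Week 12 visit + 30 | 85 + 30 = 115 | 110 to 120 | all 11 |

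Under Protocol 6.3.1 the nominal visit is 115 − 78 = 37 days after the last dose.

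**With the exclusion limited to safety data**, no Week 12 DAS28(CRP) value is lost at any last dose day, because Table 3-1 gives no upper limit for subjects who do not enter the OLE.

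**The case against.** The best defence is that the sentence was only ever meant for safety data. It follows the laboratory table, and it matches the 30-day limits in Protocol 8.6 and in the SAP definitions of treatment-emergent adverse events (7.1.5.1) and laboratory abnormalities (7.2.2.1). SAP 3.8.1 would keep the efficacy values in any case. This makes a safety-only intent plausible, and it rules out saying that the SAP simply drops Week 12 data. It does not settle the matter: the wording has no such limit, the section covers efficacy windows too, and two SAP rules give opposite answers for the same subjects.

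A reader might infer that the sentence must target efficacy, because the SAP presents no numeric laboratory statistics and no vital-sign or ECG summaries (7.2.1, 7.3, 7.5), which leaves a safety-only rule little to do. The documents do not support that step. This SAP was cut down for a synoptic report and keeps other unused text: Table 3-2 windows laboratory visits although no laboratory descriptive statistics are presented, and Table 3-1 windows weight and vital signs, which are not summarised.

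A reader might also infer that Protocol 8.6 prescribes different Week 12 efficacy tables. It does not. It governs safety analyses, and Protocol 8.5 is merely silent on a cut-off. The SAP sentence is broader than the protocol's stated limit; it does not contradict a protocol efficacy rule.

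Finally, leaving out values long after the last dose can be defended, since Protocol 3.5.2 gives these subjects standard-of-care RA treatment. That choice would have to be stated for efficacy in its own right. The SAP states no such choice.

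**Conclusion.** The point holds as a defect of scope and consistency. The 3.8.2 exclusion is not limited to safety data, it conflicts with SAP 3.8.1, and read literally it removes the Week 12 DAS28(CRP) of a non-OLE FAS subject who had the last dose at about Week 7 or earlier and stayed in follow-up. For a non-OLE completer it also excludes part or all of the follow-up visit window, depending on which protocol timing is used. These figures assume on-schedule weekly dosing and a completer's last dose on Day 78.

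The impact is minor. Enrolment stopped at 15 subjects, there is no testing, and excluded values remain in the listings. If the 15 were split evenly, a group would have 15/3 = 5 subjects, so one lost value would be a fifth of a group; the actual split is not given. It would go too far to conclude that the Week 12 results were altered or biased: the documents do not show that any subject is affected, and they give no direction.

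**What to change.** 1. In SAP 3.8.2, limit the exclusion sentence to safety data, in line with Protocol 8.6.
2. State that efficacy summaries in the FAS use all observed data in the Table 3-1 windows, with values obtained after study drug was stopped flagged.
3. Reconcile the sentence with SAP 3.8.1, so that one rule decides what enters the double-blind summaries.
4. Reconcile the follow-up visit timing in the Protocol Synopsis with Protocol 6.3.1.

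Keep the sentence that gives the follow-up visit its own label. If it covers efficacy data, as its wording allows, it already stops a late value from filling the open-ended Week 12 window. Leave the treatment-emergent adverse event and laboratory definitions unchanged.

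The SAP cost is one or two sentences and one condition in the visit-window derivation. If the SAP is already final, its Introduction provides for recording the change in the clinical study report. The one downside is that some retained values may reflect standard-of-care RA treatment given after study drug was stopped; the flag lets the reader see which.
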